4 STATISTICAL ANALYSIS

This section provides information on definitions, derivation and analysis/data presentation per domain.

4.1 Study Population

The domain study population covers subject disposition, analysis sets, protocol deviations, demographics, baseline characteristics, medical history and prior and concomitant medication.

4.1.1 Subject Disposition and Completion Status

The number of subjects who signed the informed consent will be calculated.

The number and percentage of subjects who enrolled, completed the study, remained on study and withdrew early will be summarized. The number and percentage of subjects who withdrew early for various reasons will be summarized according to the categories in the CRF. Study follow-up time and primary reason for screen failure will be summarized. Listing will also be presented.

Study Follow-up Time = EOS – training date +1

4.1.2 Analysis Sets

Effectiveness analyses will be performed using an FAS population. Demographic and baseline characteristics will be presented for both all participants analysis set and FAS. The following populations are defined:

All Enrolled Participants Analysis Set: All participating patients enrolled for the study without screen failure will be included in the All Enrolled Participants population.

Full Analysis Set (FAS): All enrolled participants with at least one non-missing post-intervention GINA guideline treatment assessment.

Based on all enrolled subjects, the number and percentage of subjects in the FAS will be calculated and summarized. Listing will be provided for the reason of exclusion from analysis sets.

4.1.3 Protocol Deviation

Major protocol deviations will be summarized for all patients in FAS. They will also be listed by each category. No patients will be excluded from analysis from the FAS due to protocol deviations.

4.1.4 Demographics

Demographics will be summarized using descriptive statistics for both all enrolled participants analysis set and FAS.

Continuous demographic variables include age, weight, height, and BMI (in kg/m²); categorical variables include age group (>65 years, ≥18 to ≤65 years, <18 years), sex, race, ethnicity, BMI group (≥24 kg/m², <24 kg/m²), education level, household per capita monthly income, occupation, residence, and source of drug purchase.

4.1.5 Baseline Characteristics

Baseline characteristics will be summarized using descriptive statistics for both all enrolled participants analysis set and FAS.

Continuous baseline variables include number of pack years (current usage only); categorical variables include nicotine usage frequency (current, former, never), temporarily stop nicotine use for more than 6 months (current usage only).

4.1.6 Disease Characteristics

Disease characteristics will be summarized using descriptive statistics for both all enrolled participants analysis set and FAS.

Disease characteristics includes Asthma history and Historical asthma exacerbation.

Continuous Asthma history variables include asthma duration since symptom start, asthma duration since diagnosed and hospital numbers for asthma clinic visit in past 12 months; categorical variables include SABA usage within one year before enrolment, Allergen Asthma Trigger, Any symptoms within the past 12 months, Most frequent symptoms within past 12 months and other symptom related questions in Asthma history CRF page.

*Asthma duration since symptom start (in months) = (ICF date – asthma symptoms start date +1)/365.25*12*

*Asthma duration since diagnosed (in months) = (ICF date – asthma diagnosed date +1)/365.25*12*

Continuous Historical asthma exacerbation variables include Historical Asthma Exacerbation number, number of exacerbations resulted in emergency room treatment, number of exacerbations resulted in hospitalization, medication number; categorical variables include Historical Asthma Exacerbation to Record within the past 12 months.

A subject data listing of disease characteristics will be provided.

4.1.7 Medical History and Concomitant Disease

Respiratory Medical History (Comorbidities) will be coded using MedDRA codes of the version currently in effect at the time of database lock. The number (percentage) of patients reporting a history of any medical condition, as recorded on the CRF, will be summarized by system organ class and preferred term in FAS. A listing of respiratory medical history will be provided.

4.1.8 Prior and Concomitant Medications

Prior and concomitant medications for asthma, and prior medications for asthma related comorbidities will be coded using the World Health Organization Drug Dictionary (WHO DD) of the version currently in effect at the time of database lock. The number and percentage of patients who took prior and concomitant medications for asthma, prior medications for asthma related comorbidities will be summarized respectively by ATC medication class 2 and WHO DD preferred term (PT) in the FAS. Prior and concomitant medications will also be presented in a listing.

Prior medications are defined as those medications with an end date prior to enrolment. Concomitant medications are defined as those medications which are taken on or after Visit 1 (Week 0). This includes medications which start prior to Week 0 but continue after Week 0. Multiple drug usage in the same classification and preferred term by a subject will be counted only once.

4.1.9 Prescriptions

Prescribed medication for asthma will be coded using the World Health Organization Drug Dictionary (WHO DD) of the version currently in effect at the time of database lock. The number and percentage of patients who are prescribed for asthma will be summarized respectively by ATC medication class 2 and WHO DD preferred term (PT) and visit in the FAS. Prescriptions will also be presented in a listing.

If treatment is prescribed at least once within 3months before Visit 0 (week -12), the subjects will be regarded as receiving this treatment at baseline. For Visit 2 (week 12), if treatment is prescribed at least once on or after Visit 1 and on or before Visit 2, the subjects will be regarded as receiving treatment at this visit. For Visit 3 -Visit 5 (week 24, 36 and 48), if treatment is prescribed at least once after last visit and on or before this visit, the subjects will be regarded as receiving treatment at this visit.

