1.3 Schedule of Activities

Table 1 Schedule of Activities (participating patients related)

Study Visit	Baseline Period	Intervention Period					Details in CSP Section or Appendix
		V1	V2	V3	V4	V5 (Study completion/ withdrawal)	
Weeks	V0	-12 ± 7	0 ± 14	12 ± 7	24 ± 7	36 ± 7	48 ± 7
Informed consent ^a	X						
Inclusion and exclusion criteria	X						Sections 5.2.1 and 5.2.2. 2
Demographics ^b	X						
Vital Sign ^c	X						
Subject status ^d	X						
Smoking status ^e	X						
Medical history (comorbidities) and medications ^f	X						
Asthma history & related treatment ^g	X						
Severe asthma exacerbation		X	X	X	X	X	
Hospitalization due to asthma exacerbation since last visit		X	X	X	X	X	Section 8.1.4
ACQ-5	X	X	X	X	X	X	Section 8.1.5.1
AQLQ(S)+12	X	X	X	X	X	X	Section 8.1.5.2
PFT	X					X	
MARS-A questionnaire	X		X	X		X	
Questionnaire of asthma knowledge for patient	X		X	X		X	
Inhale skill score for patient		X	X	X		X	

Study Visit	Baseline Period	Intervention Period					Details in CSP Section or Appendix
		V1	V2	V3	V4	V5 (Study completion/ withdrawal)	
Patient's expectation for asthma treatment	X		X	X		X	
Laboratory assessments within prior 3 months (if available in medical records) ^h	X	X	X	X	X	X	
PFT/BPT/PEF/FeNO within prior 3 months (if available in medical records)	X	X	X	X	X	X	
Medical records on asthma related assessment and treatment	X	X	X	X	X	X	
Questionnaire for Asthma Patients during COVID-19 ⁱ	X						Section 8.1.9
Patient evaluation on whose pulmonologists 1. assess symptom control, 2. watch the patient using their inhaler, educate their technique, 3. have a discussion about adherence, 4. develop or review the written asthma action plan, provide patient education, 5. had a PFT before dosage reduction	X	X	X	X	X	X	Section 6.1.2.3

PFT = Pulmonary Function Testing; BPT = Bronchial provocation test; PEF = Peak expiratory flow; FeNO = Fractional exhaled nitric oxide

- a. Informed consent must be conducted prior to performing any study procedures including data collection.
- b. Demographic includes patient age, gender, race, ethnicity and
- c. Vital signs include body mass index (BMI, calculation by height and weight)
- d. Subject Status education level, family monthly income, job, residence (urban communities or rural villages), etc
- e. Smoking status include current smoker or stopping smoking or restarting smoking, smoking pack-years

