6.7 Study Bias and Mitigation Plan

A single-arm design is chosen for its potential benefit to recruit more patients into an interventional arm instead of being randomized into a control arm. Before-intervention and post-intervention change will be described within individuals, which will reduce the variability. However, since single-arm studies do not include a direct, concurrent comparison group, their role in informing comparative effectiveness questions is not straightforward. The observed change might be impacted by the factors other than the intervention. This study might be subject to Hawthorne effect, e.g., pulmonologists and patients might change their behavior solely as a result of knowing that they are participating a study and being observed rather than as a result of the intervention. This may present a challenge to result interpretation.

There may be a hospital and patient selection bias, e.g., potential hospitals and patients can refuse to participate in this study leading to impact on the representativeness of the target hospitals and patient population. A total of around 30 hospitals will be selected in this study. To represent the diversity of patients, pulmonologists, and treatment practice in real world, hospital selection will include as many as provinces or municipalities in mainland China, where the altitude is below 1,500 meters, while balancing hospital grade (e.g. 10 Tier 2 and 20 Tier 3). Patients will be recruited in hospital outpatient setting. To minimize patient selection bias, all potentially eligible asthma patients will be consecutively approached and invited to join the study, e.g., regardless of new patients or treated, exacerbation or regular follow-up. The hospital selection and patient enrolment process will be appropriately documented.

Prior to the study intervention, there is 3-month patient recruitment period. During the 3 months, patients' health status may change and they may seek medical care due to asthma. These changes will not be captured in this study.

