9 STATISTICAL CONSIDERATIONS

9.1 Statistical Hypotheses

The change in GINA guideline-recommended treatment after guideline education and implementation, will be compared between the proportion of patients on with an ICS-based maintenance and/or reliever treatment at Week 48 and the proportion at baseline. For each treatment arm, the proportions along with the 95% confidence intervals the rates and the difference Δ will be computed. The hypothesis test is formed as follows:

The null hypothesis to be tested is:

H_0 : Proportion of patients with ICS-based maintenance and/or reliever treatment at baseline =
Proportion of patients with ICS-based maintenance and/or reliever treatment at Week 48

Against the alternative hypothesis:

H_a : Proportion of patients with ICS-based maintenance and/or reliever treatment at baseline \neq
Proportion of patients with ICS-based maintenance and/or reliever treatment at Week 48

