1.3 Number of Subjects

Approximately 1500 participants will provide 80% power at a significant level of 0.05 to detect a change from baseline in the proportion of patients with an ICS-based maintenance and/or reliever treatment at week 48 of 5%. The baseline proportion is assumed to be 40% and a within-participants correlation is assumed to be 0.25. The proportion of missing postbaseline assessment at week 48 is assumed to be 30%.

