3.1.4 Visit Window

A visit windowing strategy will be implemented for subjects as shown below.

Analysis visit	Target Day	Actual assessment day
Week 0	Day 1	Training day to D42
Week 12	Day 84	D43 to D126
Week 24	Day 168	D127 to D210
Week 36	Day 254	D211 to D294
Week 48	Day 336	D295 to D378

The visit will be missing if no assessment was reported within the specified visit window. If multiple assessments fall within one visit window, the scheduled visit takes priority, followed by the one closest to the target day. If two evaluations are equidistant from the scheduled time point, the earlier one will be used.

A visit windowing strategy will be implemented for investigator as shown below:

Analysis visit	Target Day	Actual assessment day
Baseline		<= Training day
Week 12	Day 84	Day2 to D126
Week 24	Day 168	D127 to D252

Week 48	Day 336	D253 to D378
---------	---------	--------------

The visit will be missing if no assessment was reported within the specified visit window. If multiple assessments fall within one visit window, the one closest to the target day. If two evaluations are equidistant from the scheduled time point, the earlier one will be used.

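### SAP 4.1.9 assigns no window to prescriptions between V0 and V1, so the baseline to week 48 change in ICS use includes any change that came before the QIP

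*SAP*

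**What the plan says.** **Prescription windows.** SAP 4.2.1.1 defines the primary endpoint by doctor's prescription and refers to SAP 4.1.9 for the visit definitions. There, a patient is on a treatment at baseline if it was prescribed at least once in the 3 months before V0 (week -12). The week 12 rule is "For Visit 2 (week 12), if treatment is prescribed at least once on or after Visit 1 and on or before Visit 2". For weeks 24, 36 and 48 the window runs from after the previous visit up to and including the current one. No rule is given for V1 (week 0). SAP 4.2.1.2 repeats the same scheme for medication taken, again without V1.

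**Timing of the intervention.** Training starts at a site immediately after its last patient is enrolled (Protocol 4.1, SAP 1.2). Protocol 6.7 puts a 3-month recruitment period before it, notes that patients may seek asthma care in that time, and says: "These changes will not be captured in this study".

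**What is collected.** The schedule in Protocol 1.3 marks "Medical records on asthma related assessment and treatment" at every visit including V1. Protocol section 8, on follow-up data, describes V1 to V5 collection as covering care after the intervention has started. SAP 4.1.8 counts as concomitant a medication begun before Week 0 and continued past it.

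**What is analysed.** The primary and secondary treatment summaries cover baseline and weeks 12, 24, 36 and 48. The sensitivity analysis (SAP 4.2.1.3) is a GEE model of the same endpoint. Supplementary analyses (SAP 4.2.1.4) are marked not applicable.

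**The concern.** This is a single-arm before-after study, and Protocol 6.7 itself warns of the Hawthorne effect and of factors other than the intervention. Patients are recruited consecutively in outpatient clinics, whether new or treated, in exacerbation or at routine follow-up. Some patients not on ICS may well be started on it at the enrolment contact or in the following weeks, before any pulmonologist at the site has been trained. Such a patient is a no at baseline and, if ICS is still prescribed between V4 and V5, a yes at week 48.

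The planned contrast cannot tell that patient from one whose treatment changed because of the programme. The study's stated aim is to demonstrate the benefits of the QIP, so how much of the change came before the QIP matters for reading the headline result. A second pre-intervention value is the obvious internal check on drift, and none is planned for the primary endpoint.

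**Working it through.** **1. Following one patient through the windows.** Suppose ICS is first prescribed six weeks after V0, with training at week 0, and is continued.

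| Analysis visit | Window (SAP 4.1.9) | Status |
|---|---|---|
| Baseline | 3 months before V0 | No |
| Week 0 | none defined | not reported |
| Week 12 | V1 to V2 inclusive | Yes |
| Week 48 | after V4 to V5 inclusive | Yes |

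The whole switch enters the primary change. A prescription written on the V0 day has the same fate if the word before is read strictly. SAP 3.1.2 sets the general baseline on or prior to V0 but defers to 4.1.8 and 4.1.9 for treatments.

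**2. The Week 0 analysis visit does not fill the gap.** SAP 3.1.4 defines it as "Training day to D42". It begins on the training day, so it is not a pre-QIP value.

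**3. Reproducing the planned sample size.** Inputs from SAP 1.3: "Approximately 1500 participants will provide 80% power at a significant level of 0.05"; p1 = 0.40; p2 = 0.45; within-participant correlation ρ = 0.25; 30% missing at week 48, so r = 0.70. The test is two-sided (Protocol 9.1). With (1.960 + 0.842)² = 7.849, the GEE pre/post formula on the risk-difference scale is

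n = 7.849 × [p1q1 + p2q2/r − 2ρ√(p1q1p2q2)] / (p2 − p1)²

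= 7.849 × [0.2400 + 0.3536 − 0.1219] / 0.0025 = 7.849 × 0.4717 / 0.0025 = 1481.

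On the logit scale, n = 7.849 × [1/(p1q1) + 1/(r·p2q2) − 2ρ/√(p1q1p2q2)] / (log OR)² = 7.849 × 7.887 / 0.2048² = 1476. Both agree with about 1500, and power at 1500 is 80.5%. The sample size is not in question.

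**4. What pre-training drift alone would do.** Assume no QIP effect, a rise of d points between V0 and training that persists to week 48, and the planning values for n, r and ρ. Then SE = √{[p1q1 + pq/r − 2ρ√(p1q1pq)]/1500} with p = 0.40 + d, and the test rejects with probability Φ(d/SE − 1.96) + Φ(−d/SE − 1.96).

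| d (points) | d/SE | P(significant) |
|---|---|---|
| 1 | 0.57 | 8.8% |
| 2 | 1.13 | 20.5% |
| 3 | 1.70 | 39.6% |
| 4 | 2.26 | 61.7% |
| 5 | 2.82 | 80.5% |

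The last row is the planned power, as it must be: a 5-point change from any cause gives it. It corresponds to 5/60 = 8.3% of patients not on ICS starting before training. The table shows how the test responds to drift; it is not evidence that drift of any given size will occur.

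**The case against.** The strongest reply is that the protocol already concedes this. Section 6.7 names the uncaptured 3 months, and the null hypothesis in Protocol 9.1 compares baseline with week 48 without claiming that the QIP caused the difference. That stands: the test is valid for the hypothesis as written, and the SAP contains no rule attributing the change to the programme. But disclosing the gap does not size it, and the stated aim invites a causal reading.

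Three stronger readings are tempting, and the documents do not support them.

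- A reader might infer that pre-training ICS starts will never be visible. SAP 4.1.8 and 4.1.9 plan medication and prescription listings with no window limit, so such starts could appear patient by patient. The exploratory endpoints are also blacked out in the public text, so a week 0 treatment summary there cannot be ruled out.
- A reader might infer that the data are in hand and only need tabulating. The V1 entry in the schedule and SAP 4.1.8 point that way. Protocol 6.7 and the follow-up text in section 8 point the other way, and the case report form is not available.
- A reader might infer that a window running from V0 to training would solve the problem. It could mislead. Enrolment at a site is spread over about 3 months, so that interval is near 12 weeks for early enrollees and close to zero for late ones. Late enrollees already on ICS would often have no prescription in a few days and be counted as off it. That would lower the pre-training proportion and inflate the apparent post-training gain.

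It is also fair to say that no split of this kind removes secular trend or continuing observation effects.

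**Conclusion.** The gap in SAP 4.1.9 is real and reaches the primary endpoint: the planned baseline to week 48 change mixes change before the QIP with change after it. No primary, secondary, sensitivity or supplementary analysis in the visible text reports ICS use just before training.

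The size is unknown, because the documents give no rate of pre-training starts. Rises of 1, 3 or 5 points would by themselves make the primary test significant with probability of about 9%, 40% or 81%. These figures assume no QIP effect, a net rise that persists to the V4 to V5 window, and the planned n, correlation and missingness.

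This is a weakness in interpretation that the protocol discloses but leaves unaddressed. It is not an error in the test or in the sample size, and it should be addressed before the result is described as an effect of the programme.

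**What to change.** 1. **Clarify baseline.** In SAP 4.1.9, state whether a prescription written on the V0 day counts as baseline.
2. **Reconcile the passages.** Bring Protocol 6.7 and the follow-up text in section 8 into line with the V1 treatment-record entry in the schedule and with SAP 4.1.8. State whether prescriptions between V0 and training are in the database.
3. **Add a pre-training value.** If they are, use dated prescription and medication records to class a patient as on ICS before training if it was prescribed at least once in the 3 months before the site's training date, V0-day prescriptions included. This matches the length of the baseline window. The training date is a cleaner cut than the V1 date, because V1 may fall 14 days either side of week 0.
4. **Report it.** In SAP 4.2.1.4, give that ICS proportion with a 95% CI and, descriptively, the two components of the primary change: baseline to pre-training, and pre-training to week 48. Leave the primary test and N as they are.
5. **If the records do not exist,** say so and limit any statement attributing the change to the QIP.

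The cost is SAP wording and a few descriptive rows, provided the records exist. There are three downsides. The post-training component may be smaller than the headline change. For late enrollees the pre-training window overlaps the baseline window, so pre-QIP change may be understated. And the post-training component is cleaner but still open to secular trend and Hawthorne effects.

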7.2 Participant Withdrawal from the Study

- A participating patient may withdraw from the study at any time at his/her own request, or may be withdrawn at any time at the discretion of the investigator for safety, behavioural, compliance, or administrative reasons.
- A participating patient who considers withdrawing from the study must be informed by the investigator about modified follow-up options (e.g., telephone contact, a contact with a relative or treating pulmonologists, or information from medical records).
- At the time of withdrawal from the study, if possible, an Early Study Discontinuation visit should be conducted, as shown in the SoA. See SoA for data to be collected at the time of study withdrawal and follow-up and for any further evaluations that need to be completed.

- If the participating patient withdraws consent for disclosure of future information, the sponsor may retain and continue to use any data collected before such a withdrawal of consent.

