3.1.7 Handling of Missing Data

Missing data will not be imputed unless otherwise specified elsewhere in the SAP.

Missing dates or partially missing dates will be imputed conservatively for adverse events and prior or concomitant medications/procedures.

For comorbidities, medications and prescriptions sections, incomplete (i.e., partial missing) date will be imputed.

Incomplete End Date:

If missing day and month, then December 31 will be assigned to the missing field.

If missing day only, then the last day of month will be assigned to the missing field.

If the death date is complete and the imputed end date is after the death date, then the end date will be imputed using the death date.

Incomplete Start Date/Baseline Prescribed Date

If missing day and month, then January 1 will be assigned to the missing field.

If missing day only, then the first day of month will be assigned to the missing field.

If the imputed start date is after the end date, then the start date will be imputed using the end date.

If the imputed baseline prescribed date is after the planned start date, then the baseline prescribed date will be imputed using the planned start date.

Otherwise, do not impute.

For incomplete asthma symptoms start date or asthma diagnosed date, the imputation will follow as below:

If missing day and month, then January 1 will be assigned to the missing field.

If missing day only, then the first day of month will be assigned to the missing field.

Otherwise, do not impute.

By-visit endpoints will be analyzed using observed data, unless otherwise specified. For observed data analyses, missing data will not be imputed and only the observed records will be included.

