4.2.1 Primary Endpoint

4.2.1.1 Definition

The primary endpoint is the proportion of patients with an ICS-based maintenance and/or reliever treatment, which is indicated by whether or not the treatment option includes ICS-containing medication. Change from baseline in the proportion of patients with an ICS-based maintenance and/or reliever treatment at week 48 will be analysed.

Doctor's prescription will be used to define this endpoint. The baseline and following analysis visits' definitions refer to section 4.1.9.

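### The SAP has two unreconciled rules for what counts as week 48 in the primary endpoint, so a withdrawal visit recorded as V5 could be analysed as a week-48 result

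*SAP*

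**What the plan says.** Four statements bear on the point.

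- **Protocol 1.3, Schedule of Activities.** The week-48 column is headed "V5 (Study completion/ withdrawal". It is the only column that provides for withdrawal, and asthma treatment records are among the items collected in it.
- **Protocol 7.2.** When a patient withdraws, if possible, "an Early Study Discontinuation visit should be conducted, as shown in the SoA".
- **SAP 4.1.9 and 4.2.1.1.** The treatment rule begins "For Visit 3 -Visit 5 (week 24, 36 and 48), if treatment is prescribed at least once after last visit"; the interval closes at the visit being classified. The rule pairs Visit 5 with week 48 and sets no study-day limit. SAP 4.2.1.1 then says of the primary endpoint: "The baseline and following analysis visits' definitions refer to section 4.1.9". SAP 4.2.2.2 makes the same reference for ICS-formoterol as reliever.
- **SAP 3.1.4.** Under the general considerations, "A visit windowing strategy will be implemented for subjects as shown below". Week 48 has target day 336 and window D295 to D378, and "The visit will be missing if no assessment was reported within the specified visit window".

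SAP 3.1.7 adds that, for observed-data analyses, "missing data will not be imputed and only the observed records will be included".

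**The concern.** The primary endpoint is the only one with a formal hypothesis, and its week-48 value can be derived in two ways. A programmer who follows the section that the endpoint cites would take the Visit 5 record as week 48. One who follows 3.1.4 would place a V5 record dated before D295 in an earlier window and leave week 48 missing. Because nothing is imputed, the visit label alone decides who contributes at week 48.

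On the visit-number reading, a patient who left well before week 48 could be counted as a 48-week outcome after less exposure to the programme. The observation interval would also differ, because 4.1.9 looks back to the last visit, whenever that was. Missing data would be understated, and the planned subgroup split by missing or not missing at week 48 would be misclassified in the same way.

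**Working it through.** **Step 1. The two rules on one case.** Take a patient seen at V2 on D84 who withdraws on D150, with the withdrawal visit recorded as V5.

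| | SAP 4.1.9 alone | SAP 3.1.4 windows |
|---|---|---|
| Analysis visit | Week 48 (Visit 5) | Week 24 (D127 to D210) |
| Week-48 value | Present | Missing |
| Look-back | D84 to D150, 66 days | Not stated for a reassigned record |

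The week-48 window opens 336 − 295 = 41 days before target, against ±7 days in the Schedule of Activities. A withdrawal on D295 or later, within the window, therefore counts as week 48 under either rule.

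**Step 2. Reproduce the planned sample size.** Inputs from Protocol 9.2 and SAP 1.3: p1 = 0.40, p2 = 0.45, ρ = 0.25, missing d = 0.30, power 80%, α = 0.05. Protocol 9.1 states the alternative as an inequality, so the test is two-sided. I used a pre/post GEE formula on the logit scale, keeping all baselines and losing d at follow-up:

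n = (1.960 + 0.842)² × [1/(p1q1) + 1/((1−d)p2q2) − 2ρ/√(p1q1p2q2)] / (logit p2 − logit p1)²

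= 7.849 × [4.167 + 5.772 − 2.052] / 0.2048² = 1476

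The risk-difference version gives 1481. Both agree with approximately 1500, and power at 1500 is 80.6%. The plan's figure therefore stands, on the premise that 0.30 × 1500 = 450 patients have no week-48 value and 1050 do.

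**Step 3. What mislabelling could do.** Let f be the share of the 450 with an early V5 counted as week 48, and r the ICS rate at those visits. Neither is in the documents. With a true week-48 rate of 45% and a baseline rate of 40%:

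change = (1050 × 0.45 + 450 f r) / (1050 + 450 f) − 0.40

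| f | r | Calculation | Change (points) |
|---|---|---|---|
| 0 | – | 472.5/1050 − 0.40 | 5.0 |
| 0.10 | 40% | 490.5/1095 − 0.40 | 4.8 |
| 0.50 | 30% | 540/1275 − 0.40 | 2.4 |
| 0.50 | 40% | 562.5/1275 − 0.40 | 4.1 |
| 0.50 | 45% | 573.75/1275 − 0.40 | 5.0 |
| 0.50 | 60% | 607.5/1275 − 0.40 | 7.6 |

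At r = 40%, the Step 2 formula solved for power, with ρ held at 0.25, gives 78.5% at f = 0.10 and 70.4% at f = 0.50. These are simple observed proportions, not output of the mixed model.

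**The case against.** The strongest reply is that 3.1.4 already settles the matter. It belongs to the general considerations, which apply unless otherwise stated, and 4.1.9 does not switch the windows off. Where the SAP wants 4.1.9 to replace a general rule it says so: 3.1.2 sends the baseline definition for treatments there, and 3.1.4 has no such exception. On this view 4.1.9 only supplies the look-back. The rest of the plan fits that view too, since the sample size assumes 30% missing at week 48 and a missing-at-week-48 subgroup is planned.

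Much of this stands. The windows do exist, and if applied they keep any V5 before D295 out of week 48. But 4.2.1.1 refers to 4.1.9 for the definitions of the analysis visits themselves, and a specific reference of that kind can fairly be read as stating otherwise. SAP 4.2.1.2 repeats a visit-number rule for medication taken, again without mentioning the windows. Nor does 3.1.4 say how to treat a look-back bounded by two visits.

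A second reply also stands in part. Protocol 7.2 names a separate discontinuation visit, and a shared column may show only which assessments to do. The case report form is not among the documents, so how withdrawal visits are coded cannot be seen. They also take place only if possible, and Protocol 7.3 counts unreachable patients as withdrawn, so f may be small.

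A reader might infer that early withdrawals will be analysed as week 48 and will bias the result in a known direction. The documents do not support that. It needs both the visit-number reading and V5 coding, and at r = 45% the estimate does not move. Nor do they show that the look-back would usually be under 12 weeks: it runs from the last visit, so a patient who missed visits could have a longer one.

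**Conclusion.** The point holds as an unreconciled definition. SAP 3.1.4 goes by study day, while 4.1.9, the section cited for the primary endpoint, goes by visit number, and nothing says which prevails. A V5 dated before D295 enters week 48 only if 4.1.9 is applied without the windows and withdrawal visits are recorded as V5.

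The possible effect ranges from nothing to a few points against a planned change of 5.0. The illustrated range is 2.4 to 7.6 points with half of the 450 affected, and 4.8 with one tenth affected at a 40% rate. All of these rest on assumed values of f and r and on a true week-48 rate of 45%. The sample size is not in error. The ambiguity concerns the main result and is easily removed, so it should be settled before the data are analysed.

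**What to change.** In SAP 4.1.9, with a matching reference in 4.2.1.1 and 4.2.2.2, state that:

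1. post-baseline analysis visits are determined by the 3.1.4 subject windows;
2. a V5 or withdrawal record before D295 is assigned to the window it falls in, one after D378 is not used, and neither counts as week 48;
3. the look-back interval for a reassigned record is defined explicitly. The text should also say whether a withdrawal visit counts as scheduled under the 3.1.4 priority rule, since it may share a window with a regular visit.

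Leave the baseline look-back in 4.1.9 unchanged. The 3.1.4 subject table starts at the training day and has no baseline window, so an instruction to window every record would not work for baseline prescriptions.

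The cost is a few sentences and one change to the derivation program. The change uses visit dates that the 3.1.4 windows already need, so no new data are required.
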